1. TITLE

Sign Here: How to Conduct Informed Consent with Deaf Individuals

2. EXTERNAL IRB REVIEW HISTORY*

N/A

3. PRIOR APPROVALS:

The current study is funded by the National Institute on Deafness and Other Communication Disorders (NIDCD).

The Brown University PI has been advised to consult with the IRB at his home institution, and will obtain any applicable review and/or approval from the Brown University IRB prior to his involvement in the conduct of the proposed research study.

4. OBJECTIVES*

One of the most understudied and underserved populations within our nation's healthcare system is the Deaf community – a minority group of 500,000+ people whose primary language is American Sign Language (ASL). Clinical researchers often recruit, conduct informed consent, and collect data in spoken or written English, procedures that are **linguistically inaccessible to Deaf ASL users**. Equally critical is the theoretical disconnect that occurs when healthcare providers and clinical researchers follow a medical model to “cure” or “fix” deafness, whereas most Deaf people do not want to be fixed, but rather to be respected as a cultural and linguistic minority group. This disconnect underlies a long history of mistreatment of Deaf people in the healthcare system – for example, the highly unethical sterilization of Deaf people during the 1880-1950 eugenics movement – and underlies **communal feelings of mistrust toward the medical community**.

To begin to rectify mistrust and underrepresentation in clinical research, the informed consent process has been suggested as a key area of intervention. As such, our team developed a prototype intervention to train research personnel to competently and sensitively interact with Deaf research participants during the informed consent process. Intervention development was guided by the Information-Motivation-Behavior Skills model, and executed via a two-year collaboration between UMass Chan Medical School (UMCMS) and the local Deaf community – community forums, focus groups, and a team inclusive of Deaf researchers, filmmakers, and laypeople. Although other research components could have been targeted (e.g., recruitment), our approach was modeled on the impressive success of a local collaboration that overhauled the informed consent process to increase trust between UMCMS researchers and local Black and Latinx communities.

The resulting prototype intervention – a 30-minute training film titled *Sign Here: How to Conduct Informed Consent with Deaf Research Participants* – has not yet been adapted to meet the needs of hearing healthcare providers and medical/nursing students. As such, we propose the

INVESTIGATOR STUDY PLAN - REQUIRED

following aims:

Aim 1. In Year 1, conduct formative evaluation with key stakeholders to create a new *Sign Here* training film for hearing healthcare providers.

- 1a. Conduct eight focus groups – two with UMCMS research personnel (n = 12), two with UMCMS/UMass Memorial Medical Center (UMMMC) healthcare providers (n = 12), two with Deaf professionals (n = 12), and two with Deaf community advisors (n = 12). Participants will view the prototype training film and facilitators will elicit feedback about aspects of the film that participants found helpful or unhelpful, and concrete suggestions for improving intervention delivery (e.g., film length) and/or content specific to their professional role (e.g., for providers, helping patients understand and choose between treatment options; for researchers, describing randomization, avoiding therapeutic misconception).
- 1b. Informed by Aim 1a data, perform video production to create a new training film to teach hearing healthcare providers how to better interact with a diverse group of Deaf, DeafBlind, and Hard of Hearing patients.

Aim 2. In Year 2, conduct a pilot randomized controlled trial (RCT) to test feasibility, acceptability, and preliminary efficacy of our new training intervention. 80 healthcare providers will be randomized to receive (1) the new training film or (2) an “intervention as usual” condition (i.e., standard NIH guidance on how to communicate informed consent to Deaf or hard-of-hearing individuals).

- 2a. Preliminary efficacy outcomes will be measured using medical simulation, in which each provider meets virtually with a Deaf standardized patient to conduct a simulated informed consent process via UMCMS Zoom. The Deaf standardized patient will be masked to study condition, as well as the research team members who later review and rate the recorded encounter. Following the encounter, the standardized patient and additional research team members will review the video recording of the simulation and each independently complete validated measures of provider cultural competence, communication skill, and ability to build trust with the standardized patient.
- 2b. Feasibility and acceptability outcomes include recruitment, enrollment, and retention rates; participant satisfaction; intervention fidelity; and feasibility of assessment. We will also evaluate future implementation potential via online training platforms by developing and evaluating ten content test questions that could potentially accompany an online training module. We will assess whether the intervention condition predicts content test scores, and whether content test scores predict performance on the measures of cultural competence, communication, and trust described above.

Study results will inform the design of a multi-site RCT to test the suite of *Sign Here* training interventions and potentially validate a product of immediate value – a highly-accessible, easy-to-disseminate professional-quality training film to promote inclusion of diverse Deaf individuals in our nation’s healthcare system.

INVESTIGATOR STUDY PLAN - REQUIRED

5. BACKGROUND*

A. The U.S. Deaf Community, a health disparities group of 500,000+ people who communicate via ASL, remains severely understudied and underserved within our nation's healthcare system due to language access barriers and significant mistrust of the medical community. One of the few public health efforts that employed an ASL health survey identified striking disparities within the Deaf community – compared to the general population, Deaf individuals were more likely to be obese (34.2% vs. 26.6%), to have attempted suicide in the past year (2.2% vs. 0.4%), and to have experienced physical abuse (21.0% vs. 13.9%) and forced sex (20.8% vs. 5.8%). Research on other potential disparities and how to address these disparities is lacking, in part, due to the inaccessible recruitment, sampling, and data collection procedures used in national public health surveys. For example, random-digit-dial surveys fail to sample Deaf ASL users, who use videophones rather than standard telephone technology. In-person studies often sample English speakers only and make no documentation of accommodations for Deaf signing individuals.

Deaf people's health disparities are likely exacerbated by conflicting belief systems between the medical community and the Deaf community – i.e., the medical model of deafness versus the cultural/sociolinguistic model of Deafhood. This disconnect has fueled a long history of unethical treatment of Deaf people in the healthcare system. Egregious abuses of the 19th and 20th centuries included the use of eugenics and sterilization to prevent the growth of the Deaf community. Current missteps of healthcare providers and clinical researchers include failure to provide accommodations or ASL interpreters for treatment and study procedures; an overwhelming focus on treatments and research questions meant to “solve the problem of deafness;” and failure to explain and obtain informed consent for treatment and informed consent for research in Deaf people's primary language, ASL. Together, historical mistreatment and ongoing access barriers have generated communal feelings of mistrust toward the fields of medicine and clinical research.

B. Training clinical researchers to competently and sensitively conduct informed consent with Deaf individuals is one potential starting place to begin to rectify issues of inaccessibility and mistrust. Although sometimes viewed as an administrative formality, the informed consent process is a powerful tool that fulfills a number of critical purposes – the legal purpose to protect patient rights; the ethical purpose to support patient autonomy, self-determination, and decision-making; and the interpersonal purpose to build patient-provider trust. Given these functions, the informed consent process has been suggested as a key area of intervention for increasing trust and engagement of underrepresented individuals in clinical research.

The informed consent process has similarly been identified as a research component in need of significant revamping to meet the needs of the Deaf community. In a groundbreaking commentary, Deaf researchers McKee, Schlehofer, and Thew outlined multiple reasons that standard informed consent procedures are ineffective for Deaf ASL users. For example, Deaf high school graduates demonstrate a fourth-grade median English reading level. Low health literacy is also common, with health-related vocabulary paralleling non-English-speaking U.S.

INVESTIGATOR STUDY PLAN - REQUIRED

immigrants. Yet, most informed consent protocols rely on written English forms that include medical jargon, legalistic language, and boilerplate text required by study sponsors or IRBs.

Despite commentaries on the need to adapt informed consent for Deaf ASL users and the wealth of research on culturally-appropriate informed consent for various hearing minority groups, this line of empirical work had not been extended to the U.S. Deaf population prior to our 2016 preliminary study. Via a two-year collaboration between UMCMS and the local Deaf community, our team developed a prototype film intervention to train research personnel how to conduct culturally- and linguistically-appropriate informed consent – *Sign Here: How to Conduct Informed Consent with Deaf Research Participants*. Our approach was modeled on a collaboration between UMCMS researcher, [name], and local Black and Latinx communities which resulted in a simulation-based intervention to train research staff in culturally-appropriate informed consent. Their impressive work yielded immediate positive impact and has generated four NIH-funded projects.

C. The *Sign Here* prototype training film targeted three key factors to promote clinical researchers' behavior change – providing information, eliciting motivation, and modeling behavioral skills. The Information-Motivation-Behavior Skills (IMB) model theorizes that, in order to establish a new behavior, a training intervention must inform, motivate, and teach behavioral skills to the learner. The *Sign Here* intervention was precisely tailored to incorporate these key ingredients of an effective training tool (**Figure 1**). The film spotlighted Deaf people and the use of ASL, incorporated both auditory and visual learning strategies, and leveraged humor and entertainment value to increase viewer engagement.

[figure not shown]

FIGURE 1

INVESTIGATOR STUDY PLAN - REQUIRED

D. With appropriate adaptation, the *Sign Here* training film also has the potential to improve healthcare providers' interactions with Deaf patients – a severely neglected dimension of medical and nursing education. Shortly after its completion in 2017, the *Sign Here* prototype intervention was sought out by a number of UMCMS/ UMMC departments in order to educate Emergency Medicine residents, medical and nursing students, and psychology interns about navigating clinical interactions with Deaf people. Despite high levels of perceived benefit, trainees also expressed disappointment that the training film was not tailored to their roles as current or future clinicians. They noted overemphasis on issues unique to research informed consent, including randomization, therapeutic misconception, and building disability accommodations into grant budgets. Similarly, they expressed interest in additional information unique to informed consent for clinical treatment, including strategies for describing various treatment options and supporting clients to choose between treatments, and managing the dynamics of emergency encounters in which obtaining informed consent may not be possible. By creating an adapted version of the *Sign Here* intervention to meet the distinct needs of hearing healthcare providers and medical/nursing students, the proposed study will generate an easy-to-implement training film to promote the inclusion of Deaf individuals in our nation's healthcare system.

6. INCLUSION AND EXCLUSION CRITERIA*

Our proposed aims are to create a new *Sign Here* training film for hearing healthcare providers and to conduct a pilot randomized controlled trial (RCT) to test the feasibility, acceptability, and preliminary efficacy of the new intervention. Aim 1a and Aim 2 include human subjects components and will be described separately through each relevant section below.

Aim 1a Focus Groups

Across six months, we will recruit 48 participants to eight focus groups – two groups with hearing researchers, research coordinators, and research project directors; two with hearing healthcare providers and medical/nursing students; two with Deaf research personnel, healthcare providers; and two with Deaf community members. We will continue data collection until we reach the point of saturation - i.e., the point in the research process when no new information is discovered in data analysis. As such, we propose to add up to two additional focus groups if needed to reach the saturation point: (1) medical interpreters (including hearing and Deaf interpreters) and (2) other miscellaneous stakeholders (e.g., family members of Deaf individuals, people connected to both hearing and Deaf communities). **Inclusion criteria** for all participants are: (1) age 18+; and (2) current or recent engagement in informed consent for human subjects research or clinical care.

Aim 2 Pilot Feasibility RCT

In Year 2, our team will conduct a two-arm pilot RCT to test the feasibility and acceptability of our new training intervention, as well as evaluate preliminary efficacy via medical simulation. We will recruit 80 local healthcare providers and medical/nursing students from UMCMS/UMMMC, as well as from our colleagues' collaborating institutions – Brown

INVESTIGATOR STUDY PLAN - REQUIRED

University and Harvard University. **Inclusion criteria** are: (1) age 18+; (2) current or recent engagement in informed consent for clinical care; and, (3) access to an informed consent form that can be used for a simulated informed consent session (so the participant will be familiar with the content). We will also screen participants' self-reported level of experience with Deaf people, as we aim to recruit participants with (4) little-to-no prior experience interacting with Deaf people to reflect the most probable real-word encounter that a Deaf person would have when receiving healthcare services.

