REDCap will be configured to **randomly assign** an intervention condition to each participant: (1) the new *Sign Here* training film, or (2) an “intervention as usual” control. As outlined below, prior to the study session, participants randomized to the **experimental condition** will be asked to view the *Sign Here* training film; participants randomized to **intervention as usual** will be provided with the standard NIH guidance on how to communicate informed consent to Deaf or hard-of-hearing individuals.

Recruitment materials will include a link to our **eligibility screening** survey in REDCap. Eligible individuals will be immediately directed to a second survey page that includes **eConsent** information. At the time of eConsent, REDCap will randomize the participant. Our team’s Research Liaison will then send the participant an email with the intervention appropriate to their study condition and instructions for the participant to contact our team to schedule their study session once they have completed their intervention. When scheduling for the study session, participants will be asked to come prepared with an informed consent form that they are comfortable using for the simulation and will receive a link from the study coordinator for a virtual session using UMCMS Zoom accounts. Additionally, as noted above, when participants are sent the Zoom link for their study session, the bottom of the email will include subtle contact information for “Interpreter Services.” This contact information will include the direct email address to our research team’s ASL interpreters in order to facilitate bringing an interpreter onto the Zoom call (if the participant so chooses).

Participants will be scheduled for a 1.5-hour study session on Zoom. Then, during the study session, the participant will engage in a simulated virtual encounter in which they are asked to conduct informed consent with a Deaf standardized patient (i.e., portrayed by one of our Deaf Community Advisors). The PI and Co-Is will provide intensive training to the standardized patient, including supervised role-plays, to ensure that a realistic, consistent portrayal is

INVESTIGATOR STUDY PLAN - REQUIRED

achieved. At the end of participation, all participants will be compensated with a \$100 Visa gift card.

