24. LOCAL RECRUITMENT METHODS

Aim 1a Focus Groups

Two primary **recruitment methods** will be used for hearing participants: (1) email distribution to faculty and staff; and (2) flyers posted in research and clinical buildings. We will target all departments that support human subjects research or clinical service to elicit input from personnel from various health disciplines and with varying amounts of experience. To recruit Deaf research personnel and healthcare providers, we will disseminate ASL videos and plain English flyers via Deaf-related listservs, Facebook groups, and human service agencies. The PI has used these methods successfully in six previous studies with Deaf research participants.

Aim 2 Pilot Feasibility RCT

Two primary **recruitment methods** will be used: (1) email distribution to UMCMS/UMMMC, Brown University, and Harvard University clinical faculty, staff, and medical/nursing students; and (2) flyers posted in UMCMS/UMMMC, Brown University, and Harvard University clinical buildings.

INVESTIGATOR STUDY PLAN - REQUIRED

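### Providers and students share one sample of 80, but neither the allocation nor the ANOVA uses role, which leaves avoidable chance imbalance and error variance

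*Combined protocol and SAP*

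**What the plan says.** The population of the pilot RCT is worded in two ways. In Section 4, the Aim 2 statement says "80 healthcare providers will be randomized to receive" one of the two conditions, and that sentence does not mention students. Section 6 says "We will recruit 80 local healthcare providers and medical/nursing students from UMCMS/UMMMC", adding two collaborating institutions, and Section 11 repeats this. Section 24 sends recruitment emails to a pool that includes "Harvard University clinical faculty, staff, and medical/nursing students".

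Students are not an afterthought. Section 4 itself says that the prototype film has not yet been "adapted to meet the needs of hearing healthcare providers and medical/nursing students", and Section 5 says that the adapted film should "meet the distinct needs of hearing healthcare providers and medical/nursing students". Everyone enrolled, student or not, must meet criterion "2) current or recent engagement in informed consent for clinical care" and must have access to a consent form for the simulation.

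On allocation, Section 11 has REDCap randomly assign "an intervention condition to each participant", and gives the timing: "At the time of eConsent, REDCap will randomize the participant". It states no ratio, block size or stratification factor. The screening survey, completed before randomisation, asks about professional experience, amount of prior consent experience and self-perceived consent skill.

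On analysis, Section 13 compares the arms at baseline by chi-square or ANOVA. It then compares post-intervention mean ratings between the two arms by ANOVA, with one standardised effect size per outcome. Professional role appears neither as a factor nor as a subgroup.

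**The concern.** Practising providers and students plausibly differ in how well they conduct a consent discussion, which is the performance being rated. The entry criterion on consent engagement narrows which students can enter. It does not fix how many do, and it does not separate those who conduct consent from those who have observed or assisted. The mix is therefore left to whoever answers the recruitment emails.

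If role predicts the rating, a plan that ignores it loses something in two places. At allocation, the arms can differ in student share by chance, and that difference passes straight into the unadjusted contrast. In the analysis, between-role variation stays in the error term and widens every interval. In a pilot of 80, where the effect-size estimates are imprecise anyway, this is a loss that can be avoided without enrolling anyone else. The baseline comparison in Section 13 would describe an imbalance after the fact, but the plan does not say what follows if one is found.

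**Working it through.** **Inputs.** From the documents: 80 randomised, two arms. Assumed, because the documents give no figure: 40 per arm, a student share of 30–50% (24–40 students), and a provider–student difference of 0.5–0.8 overall SDs on a rating. The plan gives no power, SD or effect size behind the 80, so there is no figure of its own to reproduce.

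**Step 1: chance imbalance.** With K students among 80 and 40 allocated to each arm, the number k in one arm is hypergeometric. The difference in student share is (2k − K)/40. A difference of at least 15 points means |2k − K| ≥ 6; at least 20 points means |2k − K| ≥ 8.

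| Students among 80 | P(≥ 15 points) | P(≥ 20 points) |
|---|---|---|
| 24 (30%) | 0.22 | 0.09 |
| 40 (50%) | 0.26 | 0.12 |

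**Step 2: typical imbalance.** Var(k) = 40 × p(1 − p) × 40/79, and the root-mean-square difference in share is 2 × √Var(k)/40.

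- p = 0.30: Var(k) = 40 × 0.21 × 40/79 = 4.25, giving 2 × 2.06/40 = 0.103.
- p = 0.50: Var(k) = 40 × 0.25 × 40/79 = 5.06, giving 2 × 2.25/40 = 0.113.

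So the typical difference is about 10–11 points.

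**Step 3: effect on the contrast.** Shift = imbalance × difference between roles.

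- Typical: 0.103 × 0.5 = 0.05 SD up to 0.113 × 0.8 = 0.09 SD.
- Tail, at 15–20 points: 0.15 × 0.5 = 0.075 SD up to 0.20 × 0.8 = 0.16 SD.

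For scale, the standard error of the standardised difference at 40 per arm is √(2/40) = 0.22, so its 95% half-width is 1.96 × 0.22, or about 0.44.

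**Step 4: outcome variance due to role.** Share = p(1 − p) × (difference between roles)².

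- Low: 0.21 × 0.5² = 0.21 × 0.25 = 0.05.
- High: 0.25 × 0.8² = 0.25 × 0.64 = 0.16.

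Adjusting for role removes that 5–16% from the error variance. The standard error is multiplied by √(1 − 0.0525) = 0.97 down to √(1 − 0.16) = 0.92, a reduction of about 3–8% before the loss of one degree of freedom.

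**Step 5: precision by role.** If 40 of the 80 were providers, split 20 per arm, the 95% half-width of their effect size would be 1.96 × √(2/20) = 0.62 SD. Such estimates can only be descriptive.

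**The case against.** The strongest reply is that chance imbalance under randomisation is not bias. Variation between roles is already part of the within-arm SD, so the ANOVA standard error already allows for it. That is right. The typical shift of 0.05–0.09 SD is also small beside a standard error of 0.22, and on the same assumptions 74–78% of allocations show no imbalance of 15 points or more. The gain on offer is modest precision, not the removal of an error.

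A second reply is that role is only a proxy. Prior consent experience is recorded more directly at screening, and the criterion seeking little prior contact with Deaf people may narrow role differences on cultural competence, communication and trust. That also has force: the 0.5–0.8 SD gap is an assumption and the true gap could be smaller. Role is still a simple two-level factor that can be known before allocation, and it matches the way the protocol describes the film's users.

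A reader might go further and infer that the effect size carried to the multi-site RCT could describe students instead of providers. The documents do not support that. Students are named as intended users in Sections 4 and 5, so the Aim 2 sentence reads as shorthand. Such a distortion would also need a different training effect in students, on which the documents say nothing; if the film works equally well in both groups, the mix does not change the mean difference. And Section 4 says only that the results will inform the later trial's design. It does not make the pooled effect size its planning value, and it does not define that trial's population.

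**Conclusion.** The point holds as a cheap improvement to design and analysis, together with a wording inconsistency. Two kinds of participant are randomised as one, and the stated allocation and model leave that information unused. The comparison is valid as planned. What is lost is a typical arm imbalance of 10–11 points in student share, equivalent to about 0.05–0.09 SD on a rating, and 5–16% of outcome variance left in the error term. These figures rest on 40 per arm, 30–50% students and a 0.5–0.8 SD gap between roles, none of which the documents state. With a smaller gap, or a very uneven mix, the gain shrinks towards nothing.

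**What to change.** - **Section 11:** record role (practising provider or medical/nursing student) as its own field at screening, and stratify the REDCap allocation by it. Use blocks within each role, since stratifying without restricting the allocation does not balance anything.
- **Section 13:** include role as a factor in the ANOVAs of the ratings. Stratifying without adjusting would leave role variance in the error term. Report the enrolled mix, and give effect sizes by role labelled as descriptive, with their intervals.
- **Section 4:** align the Aim 2 sentence with Section 6 by naming both groups.

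The cost is one allocation factor, one model degree of freedom and by-role estimates too imprecise to act on alone (half-width about 0.62 SD at 20 per arm). No extra participants are needed, and the timeline in Section 9 already includes an IRB modification before RCT recruitment that could carry these changes.
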